6.6 Supplementary/ Additional Analyses and Outcomes

The SCIENCE study will follow up with participants annually up until 16 years of age. This will be to draw inference on long-term pain and function, as well as looking at additional surgery. A separate appendix to the SAP will document the planned long-term follow-up analyses. Analysis plans for radiographic outcomes will be documented separately.

6.7 Harms

This is a low risk, pragmatic trial where both of the interventions are in common use. Thus, we do not anticipate many SAEs. All adverse events are submitted to the SCIENCE central office ONLY if they arise 12 months post-randomisation (i.e. a period deemed related to the intervention) and they fall under the category of an SAE: events resulting in Death; Life-threatening; required hospitalisation; prolonged hospitalisation; congenital abnormality of birth defect; other important medical event which may require medical or surgical intervention to prevent one of the serious outcomes listed. SAEs potentially related and unexpected are recorded on the trial's database and assessed for seriousness, causality and expectedness (Table 11).

Table 11: List of serious adverse events

| Allocation | Diagnosis | Timing of onset of event ¹ | Description of event (including signs & symptoms) | Action taken to deal with event (including any treatment) | Reason for seriousness ² | Causality: is the event related to the intervention? ³ | Expectedness (in relation to what is known about the intervention) ⁴ |
|------------|-----------|---|---|---|--|---|---|
| | | | | | | | |
| | | | | | | | |

¹: post-randomisation weeks

²: Death; Life-threatening; required hospitalisation; prolonged hospitalisation; congenital abnormality of birth defect; other important medical event which may require medical or surgical intervention to prevent one of the serious outcomes listed.

³: Possibly related; Probably related; Definitely related

⁴: Expected; Unexpected

Only unexpected SAEs potentially related to the intervention. Adverse events that are foreseeable and are not SAEs are recorded in the Complications section and are reported as outcomes.

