7.5 End of trial

The end of this trial is defined as the date all data queries have been resolved and the trial database is locked for analysis of the primary and secondary outcomes.

8. Safety Reporting

Safety reporting for each participant will begin from the first point of administration of the intervention and will end when the participant has reached their final main follow up time point, at 12 months postrandomisation. This is a low risk, pragmatic trial where both of the trial interventions are in common use. In light of this, we do not anticipate many serious adverse events (SAEs) associated with either treatment.

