8.1 Definition of Serious Adverse Events (SAE)

Serious adverse events are defined as any untoward and unexpected medical occurrence that:

- Results in death
- Is life-threatening
- Requires hospitalisation or prolongation of existing inpatients' hospitalisation
- Results in persistent or significant disability or incapacity
- Is a congenital anomaly or birth defect or
- any other important medical condition which, although not included in the above, may require medical or surgical intervention to prevent one of the outcomes listed.

NOTE: The term "life-threatening" in the definition of "serious" refers to an event in which the participant was at risk of death at the time of the event; it does not refer to an event which hypothetically might have caused death if it were more severe.

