8.2 Reporting Procedures for Serious Adverse Events

If an SAE arises in the period between randomisation and the main final follow-up time-point, that is deemed related to the trial interventions, the site will complete an SAE form and record the description, date of onset, end date, severity and assessment of relatedness to trial intervention.

For the purpose of safety recording for this trial, only unexpected SAEs potentially related to the intervention will be reported immediately to the Central Trial Team. When the local research team becomes aware of an SAE in a trial participant, the Principal Investigator (PI) will review the SAE locally and make a decision about the causality (i.e. likelihood of the event to be related/attributed to the intervention). Please refer to SAE Reporting Guidelines for details on the grades of causality. Following the assessment of causality the PI will assess any related events for expectedness. If the PI assesses the SAE as unexpected and related or potentially related, the details of the event will be entered on a SAE reporting form on the database, and the research team will notify the central trial team via email or telephone within 24 hours of the PI becoming aware of the event. Once received, causality and expectedness will be confirmed by the Chief Investigator (CI) or delegate. In the event that consensus is not reached between the PI and Nominated Person about assessment of causality and expectedness, this will be escalated to the CI for further discussion. However, if no consensus decision is reached about expectedness after further discussion within 1 working day, and the SAE is judged to be unexpected by any one of either the PI, Nominated Person or CI, the event will be classified as an Unexpected Event.

Notifying ethics bodies:

UK – All SAEs (reported from sites in the UK, Australia and New Zealand) that are deemed to be unexpected and related to the trial will be notified to the Research Ethics Committee (REC) that gave a favourable opinion of the study within 15 working days by the central trial team.

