Particular note will be made of complications related to the cast (e.g. pressure areas) or surgery (e.g. pain, wound infection, injury/irritation to the ulna nerve, implant irritation, screw cut-out, broken or retained metalwork, and the subsequent need to remove metal pins/screws), including hospital admission to manage these complications. These are summarised in the Table below.

Table 10: Comparison of complications & SAEs between treatment allocations

| | Operative fixation | Non-operative treatment | | OR (95 | 5% CI) | p- value |
|--|-----------------------|----------------------------|---|--------|--------|-------------|
| | n % | n | % | Raw | Adj. | |
| Number of complications* | - | | - | - | - | - |
| Participants with complications | | | | | | |
| Wound problems (from surgery*) | | | | | | |
| Elbow stiffness | | | | | | |
| Unable to move fingers normally | | | | | | |
| Patient Reported concerns | | | | | | |
| Unable to feel fingers normally | | | | | | |
| Ulna nerve problems (little & ring | | | | | | |
| fingers) | | | | | | |
| Other | | | | | | |
| Intra-operative complications | - | | - | - | - | - |
| Participants with intra-operative | | | | | | |
| complications | | | | | | |
| Ulna nerve injury | | | | | | |
| Fragmentation of bone | | | | | | |
| Wire breakage | | | | | | |
| Anaesthesia complications | | | | | | |
| Post-operative bleeding | | | | | | |
| Screw cut-out | | | | | | |
| Other | | | | | | |
| Immobilisation complications | - | | - | - | - | - |
| Participants with immobilisation | | | | | | |
| complications | | | | | | |
| Skin complication owing to pressure | | | | | | |
| area | | | | | | |
| Discomfort | | | | | | |
| Other | | | | | | |
| Unplanned surgery/hospital | - | | - | - | - | - |
| admissions* | | | | | | |
| Participants with unplanned | | | | | | |
| surgery/hospital admissions | | | | | | |
| Fracture fixation/ revision fixation | | | | | | |
| Removal of screw(s)/wire(s) | | | | | | |
| Planned removal | | | | | | |
| Irritation | | | | | | |
| Other | | | | | | |
| Nerve exploration (isolated | | | | | | |
| procedure) Nerve exploration & screw/wire | | | | | | |
| adjustment | | | | | | |
| Nerve exploration and grafting | | | | | | |
| Debride wound/ wound infection | | | | | | |
| Microbiological confirmation of | | | | | | |
| infection | | | | | | |
| Antibiotics prescribed | | | | | | |
| Other | | | | | | |

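### SAP harms reporting conflicts with the protocol and its own labels: planned metalwork removal sits in a tested unplanned-surgery block, one seriousness criterion is missing, and the SAE window is misworded

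*SAP*

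**What the plan says.** **Further surgery.** SAP Table 10 (section 6.1) has a block for unplanned surgery and hospital admissions. Its heading row has dashes under the odds ratio and p-value. The row beneath, counting participants with such an event, leaves those cells open to be filled. Further down the block, after the row for removal of screws or wires, come "Planned removal", irritation and other.

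**Seriousness.** Protocol 8.1 lists six criteria, one of which is "Results in persistent or significant disability or incapacity". SAP 6.7 lists the criteria twice, in its text and in footnote 2 to Table 11. Neither list contains that one.

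**Window.** SAP 6.7: "All adverse events are submitted to the SCIENCE central office ONLY if they arise 12 months post-randomisation", explained in brackets as "i.e. a period deemed related to the intervention". Protocol 8.2 requires a form "If an SAE arises in the period between randomisation and the main final follow-up time-point, that is deemed related to the trial interventions". Protocol section 8 says reporting "will end when the participant has reached their final main follow up time point", which it puts at 12 months after randomisation.

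**Start point.** Protocol section 8: "Safety reporting for each participant will begin from the first point of administration of the intervention". Protocol 8.2 starts at randomisation.

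**The concern.** Complications, including the need for further fixation, are secondary objective 5 in Protocol 6.2.2, and complications are among the core outcomes in Protocol 6.3. They are what any functional gain from surgery would be weighed against.

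If scheduled removals count as unplanned operations, the tested comparison mixes a planned part of care with a harm, and does so almost entirely in one arm. A reader of the results would see an odds ratio and p-value labelled as unplanned surgery that partly measured something else.

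The SAE definition is a matter of consistency. The SAP is the document the analyst follows, and its seriousness list and time window do not match the protocol under which sites report.

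**Working it through.** **1. Table 10.** No figure in the documents can be reproduced here, because neither document gives a rate for unplanned surgery or planned removal. The layout supports two statements: the planned-removal row lies between the unplanned-block heading and the end of that block, and no text says whether planned removals enter the participant total.

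The possible effect can be illustrated with assumed rates.

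- u = true proportion with unplanned surgery or admission, equal in both arms (assumed).
- r = proportion of the operative arm with a planned removal (assumed), independent of unplanned events. The non-operative arm is taken to have none.
- Operative-arm proportion as counted: p = u + (1 − u) × r.
- Odds ratio = [p / (1 − p)] / [u / (1 − u)]. It would be 1.0 with planned removals excluded.

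For u = 5% and r = 10%:

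- p = 0.05 + 0.95 × 0.10 = 0.145.
- Odds are 0.145 / 0.855 = 0.1696 and 0.05 / 0.95 = 0.0526, so the odds ratio is about 3.2.
- With the planned 167 per arm (SAP 3.3), that is 167 × 0.145 ≈ 24 against 167 × 0.05 ≈ 8 participants.

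Expected odds ratio over a range of assumptions:

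| True unplanned rate, both arms | Planned removal 5% | 10% | 20% |
|---|---|---|---|
| 2% | 3.6 | 6.6 | 13.5 |
| 5% | 2.1 | 3.2 | 6.0 |
| 10% | 1.5 | 2.1 | 3.5 |

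**2. Seriousness criteria.** Set against Protocol 8.1, the SAP keeps death, threat to life, hospitalisation (new or prolonged), congenital anomaly and other important events. Only disability is missing. The last item is not a full substitute, because it covers events that may need intervention to prevent a listed outcome. The reach of the omission is limited:

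- Protocol 8.3 predefines ulnar nerve injury, stiffness, instability and non-union as foreseeable complications, and includes serious ones.
- Table 10 has rows for stiffness, ulnar nerve problems, loss of finger movement or feeling, and nerve exploration.
- Table 11 is confined to unexpected SAEs potentially related to the intervention.

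What remains exposed is an unexpected, related, disabling event that meets no other criterion. It would have no seriousness code in Table 11. One loose end: the closing sentence of SAP 6.7 sends only foreseeable events that are not SAEs to the complications section, whereas Protocol 8.3 sends foreseeable SAEs there too.

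**3. Window.** Read literally, the SAP sentence admits events arising at 12 months. Protocol 8.2 covers events from randomisation up to then. Two features of SAP 6.7 show what was probably meant: the bracketed gloss describes a period, and Table 11 footnote 1 records onset in weeks after randomisation. The gloss also attaches relatedness to the period, whereas Protocol 8.2 attaches it to the event.

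**4. Start point.** First administration of treatment and randomisation are different moments, and the gap may be longer where theatre must be scheduled. The documents give no waiting times. Protocol 8.2 asks only for SAEs related to the interventions, so events before treatment starts would seldom qualify.

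**The case against.** The strongest reply is that these are drafting slips in secondary safety reporting. Much of that stands, and it rules out several stronger readings.

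- A reader might infer that SAEs from the first year are lost. The documents do not support this. What sites report is governed by the protocol, which covers the first 12 months, and the SAP's own gloss and footnote point to a missing word.
- A reader might infer that lasting nerve or elbow damage goes unreported. The foreseeable forms have rows in Table 10 whatever the Table 11 footnote says.
- A reader might infer that the two start points bias the comparison between arms. No effect is shown.
- A reader might take Protocol 5.2, which describes later removal as frequent, as a rate for planned removal. That sentence concerns removal because of skin irritation, which has its own row in Table 10. The removal rates used above are therefore pure assumptions.
- Nor is it settled that planned removals will be counted as unplanned. Indentation in Table 10 cannot be seen in the text available, and the heading carries an asterisk with no visible footnote. The planned-removal row would be shown separately, fixation or revision fixation has its own row, and SAP section 1 provides for a review of the shell tables before the final analysis.

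What does not fall is the layout itself. An analyst who follows the block as drawn could include planned removals in a tested total, and nothing in the SAP says otherwise. Counting removal as a complication agrees with Protocol 8.3; putting planned removal under an unplanned heading does not. A separate row shows the components but does not correct the total. A later review of the tables also does not replace a rule fixed in advance.

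**Conclusion.** The point holds as an inconsistency in harms reporting, minor to moderate in weight.

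The Table 10 grouping is the part with a possible inferential effect. Its size is unknown. With 5% true unplanned surgery in both arms and 10% planned removal in the operative arm, the expected odds ratio is about 3.2 instead of 1.0. Over the assumed ranges it runs from 1.5 to 13.5. These figures assume equal true rates, independence, no metalwork in the non-operative arm, and that planned removals are counted, which the SAP leaves open.

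The missing disability criterion is a definite mismatch with narrow reach. The 12-month wording is probably a dropped word that literally contradicts the protocol. The two protocol start points conflict with no demonstrated effect. Nothing shows that safety data were lost or wrongly collected, and the primary analysis of PROMIS at 12 months is untouched.

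**What to change.** - **SAP Table 10:** move planned removal to its own row outside the unplanned-surgery total, and state that it does not enter that total. Keep reporting it by arm, since Protocol 8.3 treats metalwork removal as a complication.
- **SAP 6.7 and Table 11 footnote 2:** restore the disability criterion so that both lists match Protocol 8.1.
- **SAP 6.7:** write 'within 12 months of randomisation', and attach relatedness to the event, as Protocol 8.2 does.
- **Protocol sections 8 and 8.2:** reconcile the start of the reporting window, so that one starting point is stated.

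The cost is a few words and one moved row in an updated SAP, with the reasons recorded as SAP 3.7 requires, and one protocol sentence. Table 10 already separates planned removal from irritation and other reasons, so no new data are needed.

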6.8 Health Economics and Cost Effectiveness (where applicable)

The statistician is not undertaking this analysis. A separate Health Economics Analysis Plan (HEAP) will be written by the trial health economist and all cost effectiveness analysis will be undertaken following that plan by the health economist.

7. VALIDATION OF THE PRIMARY ANALYSIS

To validate the primary outcome and key secondary outcomes a statistician not involved in the trial will independently repeat the analyses detailed in this SAP, by using different statistical software (if possible). The results will be compared, and any unresolved discrepancies will be reported in the Statistical report (See OCTRU SOP STATS-005 Statistical Report). If necessary, this will include derivation of the primary and key secondary outcomes from raw data.

Validation will be undertaken for the main model of the primary analysis only and will include: the primary outcome for analysis is PROMIS at all time points up to 12 months, and key secondary outcomes: DASH S/PA at all time points up to 12 months and EQ5D-5DY at all time points up to 12 months.

8. SPECIFICATION OF STATISTICAL PACKAGES

All analysis will be carried out using appropriate validated statistical software such as STATA, SAS, or R. The relevant package(s) and version number(s) will be recorded in the Statistical report.

9. PUBLICATION

This study will be/has been conducted as part of the portfolio of trials in the registered UKCRC Oxford Clinical Trials Research Unit (OCTRU) at the University of Oxford. It will follow/has followed their Standard Operating Procedures ensuring compliance with the principles of Good Clinical Practice and the Declaration of Helsinki and any applicable regulatory requirements.

APPENDIX: GLOSSARY OF ABBREVIATIONS

| Adverse Event |
|--|
| British National Formulary |
| Computer Adaptive Test |
| Community Health Index number (Scotland) |
| Chief Investigator |
| Case Report Form |
| Data and Safety Monitoring Committee |
| EuroQol – Youth |
| Good Clinical Practice |
| Health Economy/Economist |
| Health Economic Analysis Plan |
| |

| Study | |
|-------|--|
| | Health Technology Assessment |
| | Health Research Authority |
| | Interim Statistical Analysis Plan |
| | Missing at Random |
| | Minimally Clinically Important Distance |
| | National Institute for Health and Care Excellence |
| | Oxford Clinical Trials Research Unit |
| | Preferred Reporting Items for Systematic Reviews and Meta-Analyses |
| | Patient Reported Outcome Measurement System |
| | Quality Assurance |
| | Quality Adjusted Life Year |
| | Randomised Controlled Trial |
| | Research Ethics Committee |
| | Statistical Analysis Plan |
| | Serious Adverse Reaction |
| | Serious Unexpected Adverse Reaction |
| | Trial Management Group |
| | Trial Steering Committee |
| | Young Persons Advisory Group |
| | Study |
